11.4 Analysis of the primary variable(s)

11.4.1 Variable(s)

The primary PD endpoint will be UGE24.

The primary PK endpoints will be the C_{max}, T_{max}, AUC_{tau}, AUC_{last}, AUC_{inf}, T_{1/2}, CL/F of LIK066.

The secondary PK endpoints will be V_z/F and CL_r of LIK066.

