11.4.2 Statistical model, hypothesis, and method of analysis

The primary analyses will assess the effect of reduced renal function on UGE24 and on the PK of LIK066.

UGE24

The change from baseline in UGE24 will be analyzed using an analysis of covariance (ANCOVA) model with diabetic status, renal impaired group, day, and all associated interactions (where possible) as fixed factors and age, baseline body weight, and baseline fasting plasma glucose as covariates. Baseline fasting plasma glucose and baseline body weight will be the measurements on Day 1 0-hour. An unstructured covariance matrix will be used.

The least-square mean change from baseline will be estimated for each diabetic status by renal function by day combination. In addition, the mean difference between each renal impaired group and the group with normal renal function and the corresponding two-sided 90% confidence interval and p-value for the difference will be extracted for each diabetic status by day combination.

UGE24 will be summarized by diabetic status, renal function, and day. The change from baseline and % change from baseline will also be summarized.

The relationship between eGFR and UGE24 will be assessed graphically, separately by day.

PK

Each of the log-transformed PK parameters (C_{max} , AUC_{tau} , AUC_{last} , AUC_{inf} as applicable) will be analyzed using the same model described above for UGE24 but without the baseline covariates. For each parameter, the least-square geometric mean will be estimated for each diabetic status by renal function by day combination. In addition, the geometric mean ratio of each renal impaired group to the group with normal renal function (expressed as a percent relative difference) and the corresponding two-sided 90% confidence interval and p-value for the ratio will be extracted for each diabetic status by day combination.

Statistical analysis may be performed to compare the free fraction (f_u) across the treatment groups. If statistically significant difference exists in f_u across treatment groups, the same analysis (as planned for total parameters) will also be performed to compare the AUC_{u} and $C_{max,u}$ between treatment groups.

The summary of PK parameters is described below in [Section 11.4.4](#).

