5.1 Variables

The following pharmacokinetic parameters will be determined using the actual recorded sampling times and non-compartmental method(s) with Phoenix WinNonlin (Version 6.2 or higher) from the plasma concentration-time data:

- Primary PK endpoints: C_{max}, T_{max}, AUC_{tau}, AUC_{last}, T_{1/2}, CL/F
- Secondary PK endpoints: V_z/F and CL_r

Additional PK parameters (R_{acc}, T_{1/2acc}, C_{min,ss}, C_{av,ss}, T_{last}, C_{last} etc.) may be calculated or reported as appropriate.

The total amount of LIK066 excreted into urine (A_{e0-t}) will be used to calculate the renal clearance (CL_r) of LIK066 based on both plasma and urine data if the data allows. Plasma sample will be collected for protein binding analysis in order to determine the unbound fraction of LIK066. Accordingly, unbound PK parameters [AUC_u and C_{max,u}] may be calculated.

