5.2 Descriptive analyses

LIK066 plasma concentration data will be listed by renal function, diabetic status, subject, and visit/sampling time point. Descriptive statistics will be provided by renal function and visit/sampling time point, including the frequency (n, %) of concentrations below the LLOQ and reported as zero.

Summary statistics will include mean (arithmetic and geometric), SD, CV (arithmetic and geometric), median, minimum, and maximum. Concentrations below LLOQ will be treated as zero in the summary statistics. A geometric mean will not be reported if the dataset includes zero values.

Each of the PK parameters will be listed by renal function, subject, and day and summarized by renal function and day. Descriptive statistics will include mean (arithmetic and geometric), SD, CV (arithmetic and geometric), median, minimum, and maximum. An exception to this is T_{max} where median, minimum, and maximum will be presented.

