5.3 Statistical model, assumptions and hypotheses

The natural logarithm of each PK parameter will be analyzed using a MMRM model with diabetic status, renal function group, day, and all associated interactions (where possible) as fixed factors and age as covariate. An unstructured covariance matrix will be used.

For each parameter, the least-square geometric mean will be estimated for each diabetic status by renal function by day combination. In addition, the geometric mean ratio of each renal impaired group to the group with normal renal function and the corresponding two-sided 90%

confidence interval and p-value for the ratio will be extracted for each diabetic status by day combination.

Statistical analysis may be performed to compare the free fraction (f_u) across the renal function groups. If statistically significant difference exists in f_u across renal function groups, the same analysis (as planned for total parameters) will also be performed to compare the $AUC_{0-\infty,u}$ and $C_{max,u}$ between renal function groups. [REDACTED]

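### SAP 5.3 puts every PK parameter, and so Tmax, into the log-scale model, in conflict with protocol 11.4.2 and SAP 5.2

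*SAP*

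**What the plan says.** **The model.** SAP 5.3 opens its PK analysis with "The natural logarithm of each PK parameter will be analyzed using a MMRM model". The fixed factors are diabetic status, renal function group, day and their interactions. It continues: "For each parameter, the least-square geometric mean will be estimated for each diabetic status by renal function by day combination". The ratio of each impaired group to normal renal function follows, with a 90% CI and p-value. The visible text names no parameters and exempts none.

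**The endpoints.** SAP 5.1 gives "Primary PK endpoints: C_{max}, T_{max}, AUC_{tau}, AUC_{last}, T_{1/2}, CL/F" and "Secondary PK endpoints: V_z/F and CL_r". Protocol 11.4.1 agrees that Tmax is primary: "The primary PK endpoints will be the C_{max}, T_{max}, AUC_{tau}, AUC_{last}, AUC_{inf}, T_{1/2}, CL/F of LIK066".

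**The summary rule.** After listing arithmetic and geometric means, SD and CV for the PK parameters, SAP 5.2 adds: "An exception to this is T_{max} where median, minimum, and maximum will be presented". Protocol 11.4.4 has the same rule.

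**The protocol's model.** Protocol 11.4.2 says the log-transformed parameters "will be analyzed using the same model described above for UGE24 but without the baseline covariates". Earlier in that sentence a parenthesis names them: Cmax, AUCtau, AUClast and AUCinf, as applicable. Tmax is not among them.

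**The concern.** The SAP has dropped the list that kept Tmax out of the model. As it stands, SAP 5.2 withholds a geometric mean for Tmax and SAP 5.3 requires one.

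The statistical reason for keeping Tmax out is familiar. It is the time of the highest observed sample, so it can take only values at or near the sampling times. Actual recorded times are used, which moves values by small amounts, but they still cluster around the schedule. On the log scale, the spread within a cell, and hence the t-based interval, then reflects the spacing of the samples as well as absorption. In cells of about 5 subjects the normal approximation has little to rest on.

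At stake is how one primary PK endpoint is reported. It would carry ratios, intervals and p-values that the protocol does not call for and its data do not support well. A programmer who left Tmax out would be departing from the SAP's wording.

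**Working it through.** No figure in the plan is at issue, so the check compares the texts and counts contrasts.

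**1. Parameters covered**

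| Parameter | SAP 5.1 endpoint, so within SAP 5.3 as worded | Named in protocol 11.4.2 model | Mean given in SAP 5.2 |
|---|---|---|---|
| Cmax | yes | yes | yes |
| AUCtau | yes | yes | yes |
| AUClast | yes | yes | yes |
| AUCinf | not listed in SAP 5.1 | yes | yes, if derived |
| T1/2 | yes | no | yes |
| CL/F | yes | no | yes |
| Vz/F | yes | no | yes |
| CLr | yes | no | yes |
| Tmax | yes | no | **no** |

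SAP 5.1 has 6 primary + 2 secondary = 8 parameters, and the protocol list has 4. Three are common to both. The SAP wording therefore brings in 8 - 3 = 5 that the protocol does not name (Tmax, T1/2, CL/F, Vz/F, CLr). The protocol names 4 - 3 = 1 that SAP 5.1 does not list (AUCinf, although SAP 1.3.1 still includes it under the primary objective).

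A log scale is conventional for T1/2, CL/F, Vz/F and CLr. Tmax is the only row where the SAP's own summary rule withholds a mean, and so the only one where SAP 5.3 contradicts SAP 5.2.

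**2. Number of contrasts for Tmax**

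Inputs: 4 impaired groups (SAP 1.4), 2 diabetic statuses (SAP 5.3), 2 PK days, Day 1 and Day 7 (SAP 1.3.1).

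4 x 2 x 2 = 16 geometric mean ratios, each with a CI and p-value.

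This is an upper bound. Interactions are fitted only where possible, the severe group may have fewer than 10 subjects, and diabetic status in the normal group is matched only if possible.

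**3. Cell size**

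Protocol 3.1 expects about 50% of each impaired group to have T2DM: 10 x 0.5 = 5 per cell. With the 8 completers of protocol 11.7 it is 8 x 0.5 = 4.

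**4. What cannot be computed**

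The degree of clustering in Tmax depends on the sampling times. The assessment schedule is not in the text available, so no size can be put on the distortion of the ratio or its interval.

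**The case against.** **The wording is shorthand.** SAP 1.1 says that the SAP implements the protocol's analysis, and protocol 11.4.2 has a list. The protocol synopsis also refers to the log-transformed PK parameters without a list, evidently without meaning Tmax. SAP 5.2, immediately before 5.3, treats Tmax separately. The output shells are not visible, and SAP 5.3 ends in a redaction. An experienced programmer might well never produce these tables. This is a fair account of the probable intent. It does not remove the problem: the authors wrote a Tmax exception in 5.2 and none in the visible text of 5.3, and the literal instruction contradicts both documents.

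**Little depends on it.** No visible decision rule uses Tmax. That stands, and it keeps the point small.

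A reader might also infer two stronger claims, and neither is supported.

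- *That the model will fail because ln(Tmax) is undefined when the Day 7 pre-dose sample is the highest.* The protocol introduction gives a half-life of 10-16 h with once-daily dosing. Under simple mono-exponential decline over 24 h, the level falls to 2^(-24/16) = 0.35 of peak at 16 h and 2^(-24/10) = 0.19 at 10 h. Renal impairment could lengthen the half-life, but nothing in the documents points to a pre-dose maximum. The case is remote.
- *That one subject shifting a sampling slot would move the ratio by about 15%.* This assumes neighbouring samples at 1 h and 2 h: 2^(1/5) = 1.149 with 5 subjects. Assumed samples at 2 h and 3 h give 1.5^(1/5) = 1.084, about 8%. Neither pair comes from the documents. The figure is an unadjusted cell mean rather than the model's least-squares mean, and any parameter that doubled in one of 5 subjects would show the same 1.149. It illustrates small cells, not a fault specific to Tmax.

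**Conclusion.** The point holds as a conflict of wording with a statistical consequence. Followed literally, SAP 5.3 applies a normal-theory log-scale analysis to Tmax, a primary PK endpoint. Protocol 11.4.2 does not include Tmax in that model, and SAP 5.2 gives it no mean.

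The size is at most 16 Tmax ratios with CIs and p-values, assuming every diabetic status by renal function cell is estimable on both days. The view that these would be poorly supported rests on Tmax clustering at sampling times and on cells of about 5 subjects; its extent cannot be quantified from the documents.

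It would be wrong to infer that the PK comparison as a whole is compromised. The Cmax and AUC models, and the UGE24 analysis, do not depend on how Tmax is handled.

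**What to change.** In SAP 5.3, replace the unrestricted reference to PK parameters with the protocol 11.4.2 list: Cmax, AUCtau, AUClast and, as applicable, AUCinf. Add T1/2, CL/F, Vz/F and CLr only if the sponsor intends to model them, and say so. Because SAP 5.1 omits AUCinf, state whether it will be derived and analysed.

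Then add that Tmax is excluded from the model and reported by median, minimum and maximum, by renal function and day, as in SAP 5.2.

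A non-parametric median difference from normal renal function by day is optional. Neither document plans one, and any method chosen would have to handle ties.

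The cost is one revised sentence and one short addition, made before database lock. No new data are needed, and the sample size and the other PK comparisons are unchanged.

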1.3.1 Primary objectives

- To assess the effect of a 7-day treatment with LIK066 on 24-hour urinary glucose excretion (UGE) in subjects with decreased renal function compared to those with normal renal function
 - 24-hour urinary glucose excretion on Day 7
- To assess the pharmacokinetics of LIK066 on Day 1 and Day 7 in subjects with decreased renal function compared to those with normal renal function.
 - C_{max}, T_{max}, AUC_{tau}, AUC_{last}, AUC_{inf}, T_{1/2}, CL/F, V_z/F, CL_r

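### Unbound AUC and Cmax ratios are committed to only after a significant result from an optional free-fraction test in groups of about 8 to 10 (minor)

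*SAP*

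**What the plan says.** Both documents plan a plasma sample for protein binding. What follows from it is optional at two steps and conditional at a third.

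- **Calculation.** SAP 5.1: "Accordingly, unbound PK parameters [AUC_u and C_{max,u}] may be calculated". Protocol 8.7 says the same.
- **The fu test.** SAP 5.3: "Statistical analysis may be performed to compare the free fraction". Protocol 11.4.2 is equally optional.
- **The unbound ratios.** SAP 5.3: "If statistically significant difference exists in f_u across renal function groups, the same analysis (as planned for total parameters) will also be performed". A redaction follows in the SAP. Protocol 11.4.2 shows the same condition with no visible redaction: "If statistically significant difference exists in f_u across treatment groups, the same analysis (as planned for total parameters) will also be performed".

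The total-drug analysis has no such condition. SAP 5.3 gives each impaired-to-normal geometric mean ratio with a two-sided 90% CI and p-value, by diabetic status and day.

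The unbound AUC has two names. SAP 5.3 compares the zero-to-infinity version. SAP 5.1 and Protocol 8.7 and 11.4.2 write AUCu with no interval. The total-drug lists also differ. SAP 5.1 reads "Primary PK endpoints: C_{max}, T_{max}, AUC_{tau}, AUC_{last}, T_{1/2}, CL/F", without AUCinf, while SAP 1.3.1 reads "C_{max}, T_{max}, AUC_{tau}, AUC_{last}, AUC_{inf}, T_{1/2}, CL/F, V_z/F, CL_r", as does Protocol 2.1. Protocol 11.4.1 also counts AUCinf as primary.

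**The concern.** The study is sized for estimation. Protocol 11.7 justifies the numbers only by the width of 90% CIs, and the total-drug ratios are reported whatever they show. The unbound ratios instead depend on a significance test that was not part of the sizing. In groups this small, and with the severe group capped at 10 with no stated minimum, failure to reach significance is weak evidence that binding is the same.

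Taking unbound exposure as fu times total exposure, the unbound ratio is the total ratio times the fu ratio. An fu shift therefore carries straight into unbound exposure. If the condition is not met, the planned model-based unbound ratio and its CI are no longer promised. A reader given both point estimates could multiply them. The CI cannot be rebuilt that way, because it needs the within-subject correlation between fu and exposure.

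**Working it through.** **1. The plan's own precision figure.** Inputs from Protocol 11.7: Cmax CV 22%, 8 completers per group, two-sided 90% CI. The log-scale variance is ln(1 + 0.22²) = 0.0473, so the SD is 0.217. The half-width is t × 0.217 × √(2/8). With t = 1.895 (7 df) it is 0.206, giving 0.81 to 1.23 times the observed ratio, as stated. The UGE24 figure reproduces in the same way: 1.895 × 24 × √(2/8) = 22.7 g. With the usual two-sample 14 df (t = 1.761) the Cmax interval is 0.83 to 1.21. No stated sample-size figure is wrong.

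**2. Chance that the condition is met.** The documents give no fu CV, expected shift or (visibly) test, so these are assumptions: log-normal fu, five equal groups, a shift in the severe group only, and an overall F test.

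- σ² = ln(1 + CV²)
- λ = n × Σ(μi − μ̄)² / σ². With one group shifted by ln r, the sum is 0.8 × (ln r)².
- Probability = P(F′(4, 5n − 5, λ) > critical value)

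Example, r = 1.25, CV 20%, n = 8: 0.8 × 0.0498 = 0.0398; σ² = ln(1.04) = 0.0392; λ = 8 × 0.0398 / 0.0392 = 8.1. The 5% critical value of F(4, 35) is 2.64, and the probability is 0.548.

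| True fu ratio | fu CV | 5% level, n = 8 / 10 | 10% level, n = 8 / 10 |
|---|---|---|---|
| 1.25 | 10% | 0.995 / 0.999 | 0.998 / 1.000 |
| 1.25 | 15% | 0.821 / 0.914 | 0.899 / 0.957 |
| 1.25 | 20% | 0.548 / 0.672 | 0.680 / 0.785 |
| 1.25 | 30% | 0.262 / 0.333 | 0.386 / 0.464 |
| 1.50 | 20% | 0.984 / 0.997 | 0.994 / 0.999 |
| 1.50 | 30% | 0.748 / 0.859 | 0.846 / 0.923 |

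**3. Sensitivity to the test.** The wording could also mean contrasts of each impaired group with normal. In a simulation of 40,000 trials (ratio 1.25, CV 20%), at least one unadjusted contrast is significant in 0.64 / 0.74 of trials at the 5% level and 0.79 / 0.86 at the 10% level. If fu instead rises evenly across groups to 1.25-fold in the severe group (CV 20%, 5% level), the F test gives 0.44 / 0.55 and a linear trend test 0.69 / 0.79.

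**4. Precision if the ratio is always reported.** For Cmax,u with fu independent of total Cmax (an assumption), the log variances add. At fu CV 20%: 0.0473 + 0.0392 = 0.0865. With n = 8 and 14 df the half-width is 1.761 × √(2/8 × 0.0865) = 0.259. The interval is 0.77 to 1.30 times the observed ratio, against 0.83 to 1.21 for total Cmax. At fu CV 10% it is 0.81 to 1.23, and at 30% it is 0.73 to 1.38.

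Within a diabetic stratum, assuming an even split and pooled error df, the interval at fu CV 20% is 0.70 to 1.42 (4 per cell, 30 df) or 0.73 to 1.37 (5 per cell, 40 df).

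**The case against.** The strongest reply is that the condition is a trigger and not a bar. The fu comparison, if run, comes before it. Unbound parameters may be calculated regardless, and SAP 5.2 would then cover them: "Each of the PK parameters will be listed by renal function, subject, and day and summarized by renal function and day". No unbound parameter is a listed primary or secondary endpoint, and making an exploratory follow-up conditional is a common economy. All of this stands, and it keeps the point minor.

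Second, the size depends on assumptions. At fu CV 10%, or with a 1.5-fold shift at CV 20%, the condition is nearly always met. The overall F test is also the less favourable reading for a shift in one group, since pairwise contrasts would meet the condition more often. This stands too, which is why a range is shown.

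Third, a redaction directly follows the SAP sentence. A reader might infer that the SAP omits the test and its level. The documents do not support that, because the hidden text could hold them or could qualify the condition. The claim is therefore limited to the visible text. It survives because Protocol 11.4.2 states the same condition with nothing visibly blacked out.

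What the reply does not meet is that nothing visible commits to an unbound ratio with a CI when the test is not significant or not run.

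**Conclusion.** The concern holds as a minor improvement to a supportive analysis. On the visible text, model-based unbound ratios are promised only after a significant result from an optional test, and that test can miss a modest shift. For a 1.25-fold rise in the severe group at the 5% level, the chance of meeting the condition runs from above 0.99 (CV 10%) to 0.26 / 0.33 (CV 30%) with an F test. At CV 20% it is 0.55 / 0.67 with an F test and 0.64 / 0.74 with unadjusted contrasts. Every fu input is assumed.

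Two stronger readings are tempting. One is that unbound results will go unreported unless fu differs significantly; the optional calculation and the descriptive summaries contradict that. The other is that the primary PK comparison is compromised; the total-drug ratios are unconditional, so it is not. The naming differences are real but separate: the AUCinf mismatch concerns total drug and adds nothing to the argument about the condition.

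**What to change.** 1. Remove the significance condition from SAP 5.3, and from Protocol 11.4.2 at the next amendment.
2. For subjects with fu data, make the fu comparison firm (SAP 5.3, Protocol 11.4.2), and likewise the unbound calculation (SAP 5.1, Protocol 8.7). Otherwise the optional wording would conflict with item 3.
3. Report fu by renal function group with 90% CIs, and geometric mean ratios of unbound AUC and Cmax versus normal with 90% CIs. Label them supportive, take them from the same model as the total-drug parameters, and give them for the day or days with fu data.
4. A model pooled over diabetic status would be more precise, and SAP 6.1.3 already has one for UGE24. None is planned for PK, so if one is added, run it for total drug as well so that the two can be compared.
5. Use one unbound AUC name in SAP 5.1, SAP 5.3, Protocol 8.7 and Protocol 11.4.2, with a total-drug counterpart that is analysed. AUCtau is listed in both documents.
6. Separately, reconcile AUCinf between SAP 1.3.1, SAP 5.1 and Protocol 11.4.1.

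**Cost.** No new samples. The stratified model gives 16 unbound ratios per day with fu data (2 parameters × 4 impaired groups × 2 diabetic statuses); a pooled model adds 8. The protocol wording needs an amendment with the approvals in Protocol 13.1. The unbound CIs will be wider than those for total drug, by the amounts shown in the working.

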5.3.1 Graphical presentation of results

Arithmetic mean (SD) and geometric mean (90% CI) plasma concentration-time plots will be produced.

Overlaid individual plasma concentration-time profiles will be generated.

6 Statistical methods for Pharmacodynamic (PD) parameters

All subjects within the PD analysis set will be included in the PD data analysis.

6.1 Primary objective

The primary objective of this study is to assess the effect of a 7-day treatment with LIK066 on 24-hour urinary glucose excretion (UGE24) in subjects with decreased renal function compared to those with normal renal function.

6.1.1 Variables

The primary PD endpoint will be UGE24.

6.1.2 Descriptive analyses

UGE24 will be listed and summarized by renal function, day, diabetic status and overall. The change from baseline and % change from baseline in UGE24 will also be listed and summarized. Summary statistics for raw, change from baseline and % change from baseline in UGE24 will include mean (arithmetic and geometric), SD, CV (arithmetic and geometric), median, minimum and maximum as appropriate. Arithmetic mean (SD) plot and spaghetti plot of individuals' observed data will be produced by renal function group for overall and for each diabetic status.

Baseline UGE24 is defined to be the measurement collected on Day -1.

6.1.3 Statistical model, assumptions and hypotheses

The primary PD analysis will assess the effect of reduced renal function on UGE24.

The change from baseline in UGE24 will be analyzed using a MMRM with diabetic status, renal function group, day, and all associated interactions (where possible) as fixed factors and age, baseline body weight, and baseline fasting plasma glucose as covariates. Baseline fasting plasma glucose and baseline body weight will be the measurements on Day 1 0-hour. An unstructured covariance matrix will be used.

The least-square mean change from baseline will be estimated for each diabetic status by renal function by day combination. In addition, the mean difference between each renal impaired group and the group with normal renal function (or other least severe group with data) and the corresponding two-sided 90% confidence interval and p-value for the difference will be extracted for each diabetic status by day combination.

Additionally, the change from baseline in UGE24 will be analyzed for the overall group, using a MMRM with diabetic status, renal function group, day, and interaction terms of renal function*day and diabetic*day as fixed factors and age, baseline body weight and baseline fasting plasma glucose as covariates. An unstructured covariate matrix will be used.

